The primary outcome will be the proportion of participants who have at least one gout flare in the Allopurinol group compared with the febuxostat group during Phase 3. Flare ascertainment during Phase 3 has been deliberately chosen (rather than during Phase 1 or 2) with the understanding that gout flares are a commonly experienced physiologic consequence of ULT during the first year of therapy, and usually indicate successful urate lowering rather than treatment failure. All participants will be followed during Phase 3 regardless of the achievement of sUA goal. The primary hypothesis will test the non-inferiority of allopurinol based upon the proportion experiencing ≥ 1 flare in each of the two treatment groups in Phase 3.

Randomization:

Balanced randomization will be used to ensure that equal proportions of participants with the following characteristics are in the two treatment arms: 1) CKD Stage 3 (individuals with CKD Stages 4 and 5 will be excluded); 2) marked hyperuricemia defined as a sUA ≥ 9.0 mg/dl; 3) presence of tophi (focused examination involving the hands, elbows, feet, and ears, which are the most common sites for tophaceous deposits); and 4) participants with prior receipt of ULT. All of these factors have been associated with a lower likelihood of achieving sUA goals in recent head-to-head trials of these two agents (12, 13). Further, to guarantee enrollment of a sufficient number of gout participants with CKD stage 3 (eGFR ≥ 30 but < 60 ml/min) to address a key secondary objective (see above), we will randomize at least one participant with CKD Stage 3 for every two participants with preserved renal function (eGFR ≥ 60 ml/min).

VII. Outcome Measures

Primary Outcome:

The primary outcome will be the proportion of participants who have at least one gout flare in the Allopurinol group compared with the febuxostat group during Phase 3.

Gout flares:

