Chronic kidney disease (CKD) is defined on the basis of abnormalities of kidney structure or function that are present for >3 months and have implications for health (96). The severity of CKD is stratified based on the magnitude of reduction in glomerular filtration rate (GFR) into five categories (Table 3), with the presence of decreased GFR (<60 mL/min/1.73 m²) for >3 months defining the presence of CKD independent of other markers of kidney damage, such as albuminuria, hematuria or structural abnormalities of the kidney. Inulin, iothalamate or iothalamate clearance measurements are the “gold standards” for measurement of GFR but are highly cumbersome and are impractical in clinical practice. While creatinine clearance measurements based on 24-hour urine collections have been widely used for estimation of GFR, 24-hour urine collections are subject to numerous inaccuracies, including over- and under-collection of the urine sample. In addition, creatinine clearance systematically overestimates true GFR by 10% to 40% due to tubular secretion of creatinine. Thus, measured creatinine clearance does not improve the estimate of GFR over that provided by estimating equations (96-98). Multiple estimating equations using serum creatinine and demographic data have been developed and validated including the Cockcroft-Gault equation (99), the Modification of Diet in Renal Disease (MDRD) equation (100, 101) and the Chronic Kidney Disease Epidemiology Collaboration (CKD-EPI) equations utilizing creatinine, cystatin C or both (97, 102). In this study we will utilize the MDRD equation for estimation of GFR and assessment of kidney function. Although the CKD-EPI equation performs modestly better than the MDRD equation, particularly in patients with near normal serum creatinine values, this enhanced performance is relatively trivial in comparison to the overall precision of the equations (97, 102). More importantly, the VA utilizes standardized reporting of MDRD estimated GFR (eGFR) across all facilities.

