Patients with stage 1 or 2 CKD, based on the presence of persistent albuminuria or known structural abnormalities of the kidney (e.g. polycystic kidney disease), but with preserved kidney function with an eGFR of ≥ 60 mL/min/1.73 m², will be included in the “normal” kidney function cohort for the purpose of this study. On the basis of GFR, these patients are indistinguishable from the large numbers of healthy elderly who have an eGFR between 60 and 90 mL/min/1.73m² on the basis of age. Furthermore, significant abnormalities in renal urate and drug handling are not seen in patients with eGFR ≥ 60 mL/min/1.73 m².

Table 3: Staging of Chronic Kidney Disease based on Glomerular Filtration Rate

GFR Stage	GFR (mL/min/1.73 m ²)
1	≥90
2	60-89
3	30-59
4	15-29
5	<15

Changes in Renal Function during the Protocol

With a 950 patient study and particular in this gouty population some patients will have renal function deterioration during the study. In most cases this will not require any changes in treatment regimens with regard to ULT (allopurinol or febuxostat). However, in the case where patients develop stage 3 CKD (eGFR 30 to <60 mL/min/1.73 m²) investigators will be encouraged to stop naproxen if being used for prophylaxis and instead use colchicine 0.6 mg q day or prednisone. If patients progress to more severe stages of CKD (eGFR <30 mL/min/1.73 m²) the colchicine dose should be decreased to 0.6 mg every-other day or 0.3 mg daily or prednisone should be substituted for the colchicine. Colchicine should be avoided in patients who develop advanced CKD (eGFR <30 mL/min/1.73 m²) with concomitant hepatic dysfunction. At all times investigators will be encouraged to use their best clinical judgment.

Participant Recruitment/Enrollment:

Potential participants will be identified via a number of mechanisms including through primary care and rheumatology clinics, self-referrals, and medical record review (through use of HIPAA waiver to screen for gout diagnosis, medications used to treat gout, renal function, and uric acid level).

Several approaches will be used to identify potential participants for the study. The recruitment methods we plan on employing are as follows:

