One or more prophylactic/flare treatments including naproxen, colchicine, or prednisone will be dispensed based on prescriber judgment and individual participant need. While it is important that all participants will be on some flare prophylaxis the LSI may use their judgement if adverse events require changes or short term (≤ 10 days) interruption of the prophylactic medication. In circumstances where the LSI has additional questions or concerns the Study Chair should be consulted.

For patients with normal kidney function or mild renal impairment (defined as an estimated glomerular filtration rate [eGFR] ≥ 60 ml/min/1.73 m²), the primary options for anti-inflammatory prophylaxis will be:

- Naproxen 250 mg p.o. twice daily with the possibility of dose escalation to 500 mg twice daily for patients experiencing breakthrough flares
- Colchicine 0.6 mg p.o. once daily with the possibility of dose escalation to 0.6 mg p.o. twice daily for patients experiencing breakthrough flares OR a dose decrease (0.6 mg p.o. every other day) for patients experiencing gastrointestinal intolerance

Based on patient-specific factors about the likelihood of breakthrough flares, intolerance, or other factors, it may be appropriate to initiate naproxen and colchicine at higher or lower doses in accordance with clinical judgment.

Precautions or contraindications for the use of low-dose naproxen include: a history of NSAID or aspirin allergy, CKD Stage 3 (see below), a history of peptic ulcer disease, ongoing anticoagulation (e.g. warfarin or heparin), moderate to severe anemia, poorly controlled hypertension, or cardiovascular disease. Precautions or contraindications with the use of colchicine include the use of high-risk medications that may heighten the risk for colchicine-related toxicity, including clarithromycin, telithromycin, nefazodone, diltiazem, verapamil and certain anti-retrovirals and azole antifungals. Refer to the Drug Information Report (DIR) for more detailed information on drug interactions.

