The choice of which prophylactic agent to use (naproxen vs. colchicine) for gout patients with preserved kidney function (eGFR \geq 60 ml/min/1.73 m²) will be made at the discretion of the site investigator. A study participant may be switched to the alternative prophylactic strategy if the patient is intolerant to the first agent selected. For patients receiving naproxen, proton pump inhibitor (PPI) therapy may be considered or other effective suppression therapy for peptic ulcer disease at the discretion of the investigator. For certain patients, including those with contraindications or intolerance to both naproxen and colchicine, prednisone may be used as a second-line prophylactic agent with daily doses not to exceed 10 mg. For patients receiving prednisone, calcium/vitamin D supplementation in addition to anti-resorptive therapy may be considered at the discretion of the investigator. Prednisone should be used with caution in patients with poorly controlled diabetes mellitus.

For patients with Stage 3 CKD (eGFR of 30 to 59 ml/min), the primary option for acute gout flare prophylaxis will be:

- Colchicine 0.6 mg p.o. once daily with the possibility of a dose decrease (0.6 mg p.o. every other day) for patients experiencing gastrointestinal intolerance; note that colchicine doses exceeding 0.6 mg daily are not allowed for patients with Stage 3 CKD.
- Prophylaxis will stop for all participants at week 48.
- Low-dose naproxen will not be allowed for use in gout patients with Stage 3 CKD.
- For patients with Stage 3 CKD demonstrating contraindications or intolerance to low-dose oral colchicine, prednisone may be used as a second-line prophylactic agent with daily doses not to exceed 10 mg.

During phase 1-2 of the study, consistent with American College of Rheumatology (ACR) Gout Management Guidelines (61) the duration of prophylaxis will be the greater of:

- Six months' duration (24 weeks)
- Three months (12 weeks) after achieving a target urate goal $<$ 6.0 mg/dl for a patient without tophi at enrollment (i.e., continued prophylaxis in patients with unresolved tophi)
- Six months (24 weeks) after achieving a target urate goal $<$ 5.0 mg/dL, where there has been resolution of tophi that were present at enrollment

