- In the event that flares continue after achieving the above criteria in a given patient, prophylaxis will be continued for a minimum of three months after the flare (i.e., prophylaxis continued or restarted for patients who experience a flare).

If the above criteria for stopping prophylaxis have been met the investigator is encouraged to do so. However, in select cases, prophylaxis may be extended beyond these time frames at the discretion of the investigator until the start of phase 3.

[figure not shown]
At 48 weeks (start of study phase 3), investigators will discontinue prophylaxis for all participants who are still receiving it. Should an acute flare occur, it should be managed as discussed below and the investigator may elect to reinstitute prophylactic treatment.

Management of Acute Gout Flares During the Study:

Should a patient in the study experience an acute gout flare, the management of the case is left to the discretion of the investigating physician and/or his/her local rheumatologic consultants. For the purposes of providing guidance some broad recommendations, based largely on the recent 2012 ACR gout treatment guidelines are included below (7).

The ACR recommends that all patients experiencing acute gout flares be treated with pharmacologic intervention, ideally within 24 hours of the onset of attack. For patients who can take oral medication, NSAIDs, glucocorticoids and colchicine may all be efficacious. If the patient is experiencing a monoarticular flare in a single large joint, or the involvement of one or several small joints (e.g., toes) only, monotherapy is appropriate. If the flare is particularly severe (e.g., is polyarticular or oligoarticular involving multiple large joints), initial combination therapy with two classes of anti-inflammatory agent may be considered. The ACR does not give instructions on adjustment for co-morbidities and/or drug-drug interactions but expects that the physician will take these into account. Some of those issues are discussed further below. *A simplified schema for managing routine gout flares is provided in Figure 3.*

Figure 3: Management of routine gout flares

Standard agents

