Short-term treatment considerations for glucocorticoids include the potential for promoting hyperglycemia, hypertension, stomach ulcer (particularly in patients already on an NSAID), agitation and avascular necrosis, among others. Practitioners may want to consider using a different agent in patients at higher risk for any of these or other steroid-related complications.

Non-steroidal anti-inflammatory agents—All NSAIDs are considered to effectively treat acute gout, but these agents must be used at their maximal, anti-inflammatory doses (e.g., indomethacin 80 mg every 6 hours, ibuprofen 800 mg every 8 hours, naproxen 500 mg every 8 to 12 hours, etc.). The selection of a particular NSAID should therefore be based on availability, patient convenience, and importantly, the side effect profile of the individual NSAID in the individual patient. COX-2 selective NSAIDs (e.g., celecoxib) are also effective for gout flares at their highest dosages and may be of value in selected patients with high GI risk; addition of a concurrent proton pump inhibitor may also be a consideration, even for short-term use. The selected NSAID should be used at the maximal dose until the flare is fully resolved, then discontinued. Short-term treatment considerations for NSAIDs include the potential for promoting hypertension, renal insufficiency, gastrointestinal intolerance and peptic ulcer disease, bleeding and potentially cardiovascular events; practitioners may consider using an alternative therapy if the patient is at high risk for any of these problems, particularly if their co-morbidities (e.g., hypertension) are presently not adequately managed. The simultaneous use of an NSAID plus daily aspirin may cause more gastrointestinal intolerance than either agent alone; if these are used together a PPI is probably warranted. NSAIDs will not be used to treat acute gout flares in patients with stage 3 CKD.

Specific situations

Severe flares—as noted above, combination therapy should be considered in a patient with a particularly severe gout flare. While all three classes of agents described above can theoretically be combined, we would recommend that first consideration be given to a glucocorticoid or an NSAID plus colchicine. The combination of an NSAID and a glucocorticoid may have synergistic effects in worsening hypertension and gastrointestinal events, especially in high risk patients, and should probably be reserved for special cases.

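### For participants who develop Stage 3 CKD on study, Protocol Section IX only encourages stopping prophylactic naproxen while Section X bars it, and nothing says which rule governs

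*Protocol*

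**What the plan says.** Three parts of the Protocol bear on a participant with eGFR from 30 to just under 60 who is taking naproxen.

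- **Section IX, Changes in Renal Function during the Protocol.** When Stage 3 CKD develops on study, "investigators will be encouraged to stop naproxen if being used for prophylaxis", with colchicine 0.6 mg daily or prednisone in its place. The same paragraph ends: "At all times investigators will be encouraged to use their best clinical judgment".
- **Section X, Prophylaxis.** The list for Stage 3 CKD (eGFR 30 to 59) states: "Low-dose naproxen will not be allowed for use in gout patients with Stage 3 CKD". Colchicine is the primary option; prednisone, at no more than 10 mg daily, is second-line for contraindication or intolerance to colchicine. Earlier in the section, naproxen is a primary option only where eGFR is at least 60, and Stage 3 CKD is among the listed precautions or contraindications, with a pointer to the rule that follows.
- **Section X, Management of Acute Gout Flares During the Study.** "NSAIDs will not be used to treat acute gout flares in patients with stage 3 CKD".

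The SAP does not take up the matter.

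**The concern.** Someone who enters with preserved renal function, is given naproxen, and then develops Stage 3 CKD falls under two rules of different force. One advises stopping and leaves room for judgment; the other does not allow the drug. Section X names renal insufficiency among the risks of NSAIDs, and Section IX itself expects renal function to worsen in some participants. Yet the one sentence written for that event is the softer of the two.

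The stake is participant safety and consistent conduct. Section XVIII expects strict adherence to the protocol, but a monitor who finds naproxen continued at this eGFR cannot tell whether it is a deviation under Section X or permitted judgment under Section IX.

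**Working it through.** The plan gives no figure on this point, so the check is a comparison of text.

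**Do the two rules cover the same people?** Section IX is triggered at eGFR 30 to <60; Section X applies at 30 to 59. These are the same stage. A participant who declines into it while on naproxen meets both descriptions.

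**Is the Section X bar limited to CKD at entry?** Not in its wording. The same Prophylaxis section does tie its tophus criteria to enrollment, so its authors wrote that qualifier where they meant it. The bar on NSAIDs for flares has no entry qualifier either.

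**Do the rules differ only in force?** No. They also differ in the replacement:

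| | Section IX (on-study decline) | Section X (Stage 3 CKD) |
|---|---|---|
| Naproxen prophylaxis | Encouraged to stop | Not allowed |
| Colchicine 0.6 mg daily | One of two unranked choices | Primary option |
| Prednisone | One of two unranked choices, no dose cap | Second-line, at most 10 mg daily |
| NSAID for a flare | Not addressed | Not to be used |

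**What follows if the Section IX wording is taken alone?** Prophylactic naproxen may go up to 500 mg twice daily (Section X), which is 2 × 500 = 1,000 mg a day. The flare guidance gives 500 mg every 8 to 12 hours; at 12 hours that is also 2 × 500 = 1,000 mg a day. Section IX would then leave room for a daily dose that Section X does not permit for even a short flare course at the same eGFR.

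**Who could be affected?** Only participants who enter with eGFR of at least 60, take naproxen rather than colchicine, and then decline. The documents bound only the first of these groups: 950 − 317 = 633 if about 317 enter with Stage 3 CKD (Section VII), or fewer than 950 / 2 = 475 if over half do (Section VIII, Secondary Data Analysis). These are ceilings on the entry pool and do not estimate the number affected, which the documents do not give.

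**The case against.** The strongest answer is that the two passages can be reconciled. Section IX may be the specific rule for CKD that arises on study, and Section X the rule for CKD at entry; there is then no contradiction, only a choice to leave discretion. Alternatively, if the Section X bar does reach these participants, naproxen is already forbidden, and encouraging an investigator to stop does not license continuing. Either reading is tenable. The documents adopt neither, and the first produces the odd result that daily naproxen may be tolerated where an NSAID for a flare is not.

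A reader might go further and infer a measurable period of excess naproxen exposure. Section IX defines CKD by a reduced GFR "for >3 months defining the presence of CKD independent of other markers of kidney damage", so an investigator might wait for confirmation, or simply continue until prophylaxis ends. The documents do not support putting weeks on this. Section IX gives its on-study trigger as an eGFR range with no duration, as do Section VI (Randomization) and Section X, and no passage tells an investigator to wait. Any such range would rest on assumed behaviour, and indefinite continuation would breach the Section X bar if that bar applies.

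A reader might also infer that one eGFR below 60 should force a switch. That is a debatable clinical trade-off: Section IX acknowledges the limited precision of the estimating equations, and a small dip may be transient. The inconsistency can be removed without settling it.

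It is also fair to say that creatinine is monitored throughout, that colchicine is an equal first choice at eGFR of at least 60, and that many investigators would probably stop naproxen unprompted. These points keep the matter small.

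**Conclusion.** The point holds as a conflict between two rules on participant safety, and it is minor. For participants who develop Stage 3 CKD on study, Section IX is softer than the bars in Section X, ranks the substitutes differently, and no text says which governs. This rests on reading Section X as written, without an implied limit to CKD at entry.

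No number of affected participants and no exposure time can be given. Nor should a reader infer an effect on the trial's main result: prophylaxis is withdrawn before the primary observation period ("At 48 weeks (start of study phase 3), investigators will discontinue prophylaxis for all participants who are still receiving it"). Section X lets the investigator restart it only after a later flare. Sample size, power and alpha do not depend on this wording.

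**What to change.** In Section IX, replace the sentence that encourages stopping naproxen with a requirement, and align the substitutes with Section X. Suggested wording: *A participant taking naproxen for prophylaxis will be taken off it and given colchicine 0.6 mg once daily or, where colchicine is contraindicated or not tolerated, prednisone at no more than 10 mg a day, as in Section X.* The sponsor should decide, and say, whether a borderline first value may be repeated before the switch.

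Limiting the Section X bars to CKD at entry would also remove the conflict, but it would give less protection to participants whose function declines.

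The cost is one sentence in a protocol clarification and a letter to sites, with no new tests or visits. The downside is that a few participants lose naproxen and take colchicine, with its drug-interaction precautions, or prednisone, with its caution in poorly controlled diabetes; both cautions are already in Section X.
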